## **16.0 Potential Benefits to Subjects**

Subjects in the omega-3 supplement arm will receive the investigational product at no cost. (Those in the placebo arm will receive placebo at no cost.). Participants will also receive two free blood spot tests measuring omega-3 levels: one at baseline, and one at the end of the 12 weeks of the study.

Overall, the potential benefits to society of this feasibility study is to determine if a larger study on omega-3 supplementation for recovery of Long Covid Syndrome is warranted.

## **17.0 Data Management and Confidentiality**

### **17.1 Data analysis plan**

All study data will be summarized with descriptive statistics. Continuous variables will be summarized with means, standard deviations, medians and ranges. Categorical variables will be summarized with counts and percentages. Data will be summarized overall and separately by the two study arms: Omega-3 supplement or placebo. In general, continuous endpoints will be compared between groups using t-tests or Wilcoxon rank sum tests, as appropriate. Categorical endpoints will be compared between groups using chi-square tests or Fisher's exact tests, as appropriate.

The primary analysis will be the comparison of groups on the long covid-19 symptoms recovery using a chi-square test or Fisher's exact test, as appropriate.

Additional exploratory analyses may be conducted to better understand relationships within the data.

Results with a p-value less than or equal to 0.05 will be considered statistically significant. No adjustments for multiple comparisons will be implemented as this is a feasibility study not statistically powered for analyses.

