## **2.0 Objectives**

### **Primary Objective**

To determine the feasibility of a clinical trial for omega-3 supplementation v. placebo in medical center team members for post-covid recovery.

This will serve as a proof-of-concept for a future, grant-funded study to evaluate the efficacy of omega-3 supplementation among a larger population recovering from covid-19.

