## **4.0 Study Endpoints**

### **4.1 Primary Outcome Variables**

The primary endpoint is evaluation of feasibility and acceptability of omega-3

supplementation v. placebo to limit post-covid syndrome among adult patients. The Follow-up Feasibility Survey (Appendix D) will be used for this analysis.

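### Feasibility is the primary endpoint, but section 17.1 gives it only summaries and a between-arm test, with no interval or progression bound, so no result is pre-specified as showing that the larger trial is not feasible

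*Combined protocol and SAP*

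**What the plan says.** Section 2.0 gives the primary objective: "To determine the feasibility of a clinical trial for omega-3 supplementation v. placebo in medical center team members for post-covid recovery". Section 4.1 follows it: "The primary endpoint is evaluation of feasibility and acceptability of omega-3" supplementation against placebo, and "The Follow-up Feasibility Survey (Appendix D) will be used for this analysis". Section 16.0 gives the purpose as being to "determine if a larger study on omega-3 supplementation for recovery of Long Covid Syndrome is warranted".

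Section 17.1 is the only analysis plan. Its provisions that reach the Appendix D items are:

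- **Description.** "Categorical variables will be summarized with counts and percentages", and "Data will be summarized overall and separately by the two study arms".
- **Inference.** "Categorical endpoints will be compared between groups using chi-square tests" or Fisher's exact test; continuous endpoints get a t-test or Wilcoxon test between arms. Significance is at p ≤ 0.05, and the study is declared not powered.
- **Primary analysis.** The comparison named as primary is of symptom recovery between arms.

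Appendix D mixes formats. It has Yes/No/Neutral items (instructions clear, pills easy to take, interference with daily life), a Yes/No item on skipped doses, a five-level satisfaction scale, days per week of pill-taking, and free text.

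**The concern.** Feasibility is a question of level: did enough subjects take the capsules, stay in the study and find it acceptable? A test of omega-3 against placebo asks whether the arms differ, and the answer can be no at any level, good or bad. The one inferential method that reaches the primary endpoint is therefore aimed at a different question, and the analysis labelled primary concerns a different endpoint.

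The decision on a larger study is at stake. With no bound set beforehand, it would rest on judgement after the data are seen, or drift towards an unpowered symptom p-value because that is what 17.1 calls primary. A bound chosen afterwards can be placed so that the observed rate passes.

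**Working it through.** **Inputs.** 50 subjects per arm, 100 for analysis, up to 120 recruited (section 12.0); p ≤ 0.05 (section 17.1), taken as two-sided because sidedness is not stated. The documents give no feasibility rate, threshold or precision target, so there is no planned figure to reproduce. All rates below are assumptions. Each treats an item as already split into yes and no, which the plan does not do.

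**1. Does the planned test respond to the level?** For counts a/50 and b/50, the chi-square statistic without continuity correction is 100·[a(50−b) − b(50−a)]² / [50·50·(a+b)·(100−a−b)].

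| Arm counts | Overall | Chi-square statistic | Chi-square p | Fisher p |
|---|---|---|---|---|
| 15/50 v 15/50 | 30% | 0 | 1.00 | 1.00 |
| 45/50 v 45/50 | 90% | 0 | 1.00 | 1.00 |
| 50/50 v 44/50 | 94% | 100·300²/(2500·94·6) = 6.38 | 0.012 | 0.027 |
| 5/50 v 4/50 | 9% | 100·50²/(2500·9·91) = 0.12 | 0.73 | 1.00 |

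The first two rows cannot be told apart. The last two run against intuition: the excellent result is significant and the dismal one is not. With equal true rates of 10%, 30%, 50%, 70% or 90% in both arms, full binomial enumeration gives a chance of p ≤ 0.05 of 5.0% to 5.7% for chi-square and 1.8% to 3.5% for Fisher. The p-value carries almost no information on the level.

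**2. Is there a bound elsewhere?** The nearest candidates are:

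- the enrolment period in section 9.0, which is a forecast;
- the non-compliance rule in sections 6.2 and 14.0, which removes individuals and sets no study-level limit;
- the look at the first 20 subjects in section 6.2, which has no numerical criterion;
- the adverse-event stop in section 15.0, which is a safety rule.

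None states a level of accrual, retention, adherence or acceptability that would count against a larger study.

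**3. Could the planned size support a bound?** Exact (Clopper-Pearson) 95% intervals are 70.8% to 87.3% for 80/100 and 66.3% to 90.0% for 40/50. Take as an illustration a 'go' that requires the lower limit to exceed 70%. Since 79/100 has a lower limit of 69.7%, the smallest passing count is 80. With X ~ Bin(100, p), P(X ≥ 80) is:

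| True rate | 70% | 75% | 80% | 85% |
|---|---|---|---|---|
| P(go) | 1.6% | 14.9% | 55.9% | 93.4% |

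A true rate equal to the cut-off is close to a coin toss. Several measures compound this: four independent measures, each truly at 85%, would all pass with probability 0.934⁴ = 0.76.

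**4. Does the denominator matter?** Section 6.2 (item 8) places the feasibility survey at the end of participation. Subjects who stop early get the Study Discontinuation Verification form, whose three questions cover discontinuation, pills remaining and disposal, with nothing on acceptability. If 120 are recruited and 100 finish, 80 favourable answers are 80% of finishers but 80/120 = 66.7% of recruits, exact 95% interval 57.5% to 75.0%. The same 80 answers pass the illustrative rule on one denominator and not on the other.

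**The case against.** The strongest reply is that 17.1 already plans overall counts and percentages. A reader might infer from the missing bound that no possible result could show the larger trial to be infeasible. The documents do not support that: if 30% found the pills easy to take, the 30% would be reported, and judgement after the fact can still be negative. What stands is narrower. No result has been designated in advance as unfavourable, and the percentage would come without an interval.

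A reader might also infer that the between-arm comparison should go. Sections 2.0 and 4.1 both frame feasibility as omega-3 against placebo, and a difference in acceptability between arms is useful when planning a placebo-controlled successor. The comparison can stay; it cannot stand in for the level.

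A third reply is that this is a feasibility study, openly unpowered, and that 17.1 speaks only of what is done in general. The first part argues for estimation against set bounds rather than for p-values. The second leaves room for another method but names none.

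Finally, any threshold quoted here is arbitrary, since the documents offer none. That is correct, and it is why the rule above is only an illustration.

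**Conclusion.** The concern holds in this form: the primary endpoint has descriptive summaries and a between-arm test, but no interval, no progression bound and no place as the primary analysis. The test gives p = 1.00 at both 30% and 90% in each arm, so it cannot supply what section 16.0 asks for. A very poor rate would be seen, but the plan does not say what rate is poor enough to matter.

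The gap lies in the plan, not in the sample size: 100 subjects give intervals of roughly ±8 to 9 percentage points around 80%. The data would remain usable, so this is a change that should be made rather than a fatal flaw. The conclusion that no bound exists rests on the text alone. The numerical illustrations rest on assumed rates, a yes/no split of each item, 100 analysed subjects and, for the combined figure, independence between measures.

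**What to change.** Amend section 17.1 as follows:

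1. Make feasibility and acceptability the primary analysis, in line with section 4.1, and move symptom recovery to secondary, in line with section 4.2.
2. Name the measures (for example accrual, retention, adherence, survey and blood-spot completion, and the chosen Appendix D items), and define for each what counts as a success, including how Neutral answers and the satisfaction scale are split.
3. Report each proportion overall and by arm with an exact 95% interval. Use all randomised subjects as the denominator where the measure allows. Where only finishers can answer, say so and show the retention rate beside it.
4. Keep any between-arm comparison of these measures as descriptive.
5. State go, revise and stop bounds before enrolment, say how several measures combine into one decision, and show the probability of 'go' over a range of true rates. The values are for the sponsor to set.

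The cost is about a paragraph in 17.1 and one agreed set of bounds, with no additional subjects. Adding acceptability items to the discontinuation form would help the denominator but is optional. The real price is that the sponsor commits in advance to a result that could stop the follow-on trial.

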## 1.0 Study Summary

Study Title	HMH Omega-3 Covid Recovery Study
Study Design	We will conduct a two-arm, double blind randomized 12-week study to supplement omega-3 (EPA + DHA) among 100 adults (age 18+) who had covid-19 and are experiencing possible after-effects from the illness (post-acute sequelae of covid-19, also called post-covid syndrome or long covid syndrome).
Primary Objective	The primary objective is to serve as a feasibility study for omega-3 fatty acid supplementation v. placebo in adult patients to limit long covid syndrome. This will serve as a proof-of-concept for a larger follow-up study to subsequently be conducted.
Secondary Objective(s)	Determine which of the post-covid symptom(s) are most impacted by omega-3 supplement.
Research Intervention(s)/Investigational Agent(s)	Participants will be assigned to one of two study arms and asked to take an Omega-3 supplement or placebo for 12 weeks. Participants will report symptoms bi-weekly throughout the study period. A spot blood sample to assess omega-3 levels will be done at baseline and at the end of the 12-week study period.  A survey will be used bi-weekly to assess health status and outcomes via patient self-report. Data on demographics and comorbidities such as obesity and diabetes will be collected at baseline. At the end of study participation, subjects will take a follow-up survey assessing feasibility.
IND/IDE #	IND # 157250
Study Population	Hackensack Meridian Health team members age 18+ who tested positive for COVID-19 28+ days prior and who are not already taking an Omega-3 supplement.
Sample Size	50 participants in each arm = 100 total for final analysis (up to 60 participants in each arm will be recruited if needed, dependent on attrition for a total of up to 120)
Study Duration for individual participants	Individual participants will be in the study for 12 weeks. During the 12 week study period, subjects will be sent a survey every two weeks. At the end of the 12 weeks, subjects will complete a short survey collecting feasibility and acceptability data.
Study Specific Abbreviations/Definitions	
 
• Hackensack Meridian Health (HMH)
 
• Center for Healthy Senior Living (CHSL)
 

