#### **4.2 Secondary and Exploratory Outcome Variables**

A separate analysis will be conducted to determine which post-covid symptom(s) are more impacted by omega-3 supplement. The Bi-weekly Symptoms and Quality of Life Post Covid-19 Survey (Appendix C) includes the four symptoms being measured (respiratory, fatigue, lack of taste, lack of smell). Therefore, this bi-weekly survey will be used for this efficacy analysis.

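### Section 17.1 makes a between-arm test of symptom recovery the primary analysis, but the primary endpoint is feasibility and acceptability from Appendix D, which has no symptom-recovery item

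*Combined protocol and SAP*

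**What the plan says.** The sections that set the aims put feasibility first.

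- Section 1.0: "The primary objective is to serve as a feasibility study".
- Section 2.0, Primary Objective: "To determine the feasibility of a clinical trial for omega-3 supplementation v. placebo". Efficacy in a larger population is left to a later, grant-funded study.
- Section 4.1: "The primary endpoint is evaluation of feasibility and acceptability of omega-3" supplementation versus placebo. The instrument is named: "The Follow-up Feasibility Survey (Appendix D) will be used for this analysis". Only this section adds acceptability to the primary endpoint and ties it to Appendix D; 1.0 and 2.0 state the primary objective as feasibility alone.

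Symptom effects rank lower. They are the secondary objective in section 2.0. Section 4.2, on secondary and exploratory outcomes, says: "A separate analysis will be conducted to determine which post-covid symptom(s) are more impacted by omega-3 supplement". The source is Appendix C: "Therefore, this bi-weekly survey will be used for this efficacy analysis".

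Section 17.1 reverses this order: "The primary analysis will be the comparison of groups on the long covid-19 symptoms recovery", tested by chi-square or Fisher's exact test. It never mentions feasibility or acceptability as an endpoint. It applies a significance limit of p ≤ 0.05 and declines any multiplicity adjustment because "this is a feasibility study not statistically powered for analyses".

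**The concern.** The analysis plan and the endpoint section name different primary questions, answered from different instruments. An analyst following 17.1 would report an efficacy p-value as the trial's primary result, although 4.2 calls that comparison secondary or exploratory and 17.1 itself says the study is not powered. Whether significant or null, that p-value could be read as the headline finding.

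Meanwhile the question the trial was set up to answer would have no designated analysis. The generic between-arm tests in 17.1 do not fill the gap, because they ask whether the arms differ and not how feasible or acceptable the regimen is.

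Timing adds to the risk. Section 6.2 plans an interim analysis of the first 20 subjects, and section 8.0 has the team look at each completer's data before telling that subject the assignment. If two candidate primaries stay open, the choice between them could be made after results have been seen.

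**Working it through.** **1. Compare the sections.** The claim is a consistency check and needs no arithmetic.

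| Item | Sections 2.0, 4.1 and 4.2 | Section 17.1 |
|---|---|---|
| Primary question | Feasibility (4.1 adds acceptability) | Symptom recovery, arm against arm |
| Data source | Appendix D | None named; 4.2 assigns symptoms to Appendix C |
| Rank of symptom effects | Secondary/exploratory | Primary |
| Analysis of feasibility | Appendix D survey | Generic descriptives and between-arm tests only |

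**2. Can the named analysis be run on the primary instrument?** The Appendix D follow-up survey asks about clarity of instructions, missed doses, ease of taking the pills, interference with daily life, satisfaction, willingness to be contacted again, new diagnoses and vaccination, with free-text comments. Nothing asks whether breathlessness, cough, fatigue, or loss of taste or smell has resolved. Symptom status is collected in Appendix C. The answer is no.

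**3. Do the generic tests answer the feasibility question?** Take two hypothetical results on the satisfaction item:
- 45/50 v 45/50 satisfied (90% in each arm): Fisher p = 1.0
- 25/50 v 25/50 satisfied (50% in each arm): Fisher p = 1.0

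The test cannot tell a well-accepted regimen from a poorly accepted one. The planned counts and percentages do show the level, but without an interval.

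**4. Illustration: what the recovery test can detect.** The plan gives no recovery rate, effect size or power, so its sample size cannot be reproduced. Inputs: 50 per arm (section 12.0); alpha 0.05 (17.1), taken as two-sided because the plan does not say; placebo recovery p₁ assumed at 5–50%. With p₂ = p₁ + d and p̄ the mean of the two, the normal approximation is

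power = Φ{[d√n − 1.96√(2p̄(1−p̄))] / √(p₁(1−p₁) + p₂(1−p₂))}.

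Example with p₁ = 0.20 and d = 0.20: (1.414 − 1.270)/0.632 = 0.228, and Φ(0.228) = 0.59.

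| Assumed placebo recovery | Gain for 80% power: normal | Gain for 80% power: Fisher | Power for +20 points: normal | Power for +20 points: Fisher |
|---|---|---|---|---|
| 5% | 0.197 | 0.214 | 0.809 | 0.748 |
| 10% | 0.227 | 0.243 | 0.711 | 0.640 |
| 20% | 0.260 | 0.280 | 0.590 | 0.515 |
| 30% | 0.275 | 0.290 | 0.533 | 0.463 |
| 40% | 0.276 | 0.290 | 0.516 | 0.462 |
| 50% | 0.267 | 0.283 | 0.533 | 0.463 |

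This agrees with the plan's own statement that it is not powered.

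**5. Illustration: precision for a feasibility item.** Half-width = 1.96√(p(1−p)/n), with p assumed.

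| Assumed rate | n = 100 (both arms) | n = 50 (one arm) |
|---|---|---|
| 60% | 0.096 | 0.136 |
| 80% | 1.96√(0.16/100) = 0.078 | 1.96√(0.16/50) = 0.111 |
| 90% | 0.059 | 0.083 |

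These assume that everyone analysed returns Appendix D; non-response would widen them.

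**The case against.** The strongest reply is that the gap is mostly one of labelling. Section 17.1 promises descriptive statistics for all study data, overall and by arm, which covers every closed-response item in Appendix D. For a feasibility study that is usable. No sample size, alpha split or go/no-go rule hangs on the word primary. The sentence might also be read as naming the main hypothesis test within an otherwise descriptive plan.

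Part of this stands. The Appendix D levels would be reported, and the power figures add little to what the plan already concedes. But the text does not say that the sentence concerns hypothesis tests only, and the label decides which result is presented as the trial's answer.

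Two further objections are fair but separate. First, confidence intervals alone do not say what level of acceptability is enough, and the plan gives no threshold. Second, relabelling does not make the symptom comparison sound. Recovery is undefined in 17.1. The stop-week choices in Appendix C end at the fourth week after diagnosis, while the inclusion criteria require symptoms lasting more than 12 weeks. The sponsor could also resolve the conflict the other way, by making symptoms primary, but that would mean rewriting 1.0, 2.0, 4.1 and 4.2 around a comparison the plan calls unpowered.

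**Conclusion.** The concern holds and must be fixed. In current text, the analysis named as primary does not address the primary endpoint and cannot be run on the instrument assigned to that endpoint. This rests on the wording of 1.0, 2.0, 4.1, 4.2, 17.1 and Appendix D, and on no assumed rate.

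The figures only give scale. Over assumed placebo recovery of 5–50%, with a two-sided test, a 20-point gain would be detected with about 52–81% power by the normal approximation, or 46–75% by exact Fisher. Over assumed rates of 60–90% and full response, feasibility proportions would have half-widths of about 6–10 points overall and 8–14 points by arm. The trial can therefore describe its stated primary endpoint with moderate precision, while the test now labelled primary would be reliable only for large effects.

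**What to change.** Amend section 17.1 in two places.

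1. State that the primary analysis is estimation of the Appendix D feasibility and acceptability items, each as a proportion with a 95% confidence interval, overall and by arm.
2. Relabel the symptom-recovery comparison as secondary or exploratory, to match 4.2, and report it as a difference in proportions with a 95% confidence interval. Do not present it as the trial's primary result.

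Retention or survey completion may be added as primary measures only if 4.1 is amended to match. The definition of recovery, the Appendix C response options and any feasibility threshold need their own attention; this change does not settle them.

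The cost is a short amendment with IRB approval before implementation, as section 20.1 requires. The relabelling and the Appendix D estimates need no new data collection. What is lost is a primary efficacy p-value from a comparison the plan already describes as unpowered.

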## **8.0 Sharing of Results with Subjects**

Individual-level data (the results of both COVID-19 tests and the omega-3 levels from the blood draw if applicable) will be shared with participants. The major findings of the study and aggregate data, will be shared with participants after the study has concluded.

1) Unblinding will occur when a subject drops out of the study due to an adverse event. The subject will be informed of their study arm assignment via email so that they can better understand any possible adverse reaction to the study medication.

2) Subjects who complete the study will be unblinded and informed of their study arm assignment via email after the study team has seen their data (descriptive statistics generated by RedCap). This will be done within 4 weeks of each subject finishing the study.

The study coordinator will inform each subject when they finish study participation, to expect an email advising which study arm they were in.

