## 10.0 Inclusion and Exclusion Criteria

### Inclusion Criteria

- Team member at Hackensack Meridian Health
- Age: 18+
- Willing to provide informed consent
- Formal diagnosis of COVID-19 via PCR test (if home test was done, team member must confirm via PCR test)
- Outpatient treatment only for covid-19; no hospitalization (most team members will be vaccinated and may likely have milder case)
- Must be experiencing 1+ ongoing covid-19 symptom being measured in this study (respiratory symptoms (shortness of breath, cough), fatigue, loss of taste, loss of smell)
- Symptom(s) have persisted for more than 12 weeks after initial infection

- Symptom(s) coincided with covid-19 infection and were not present prior to covid-19 infection
- Does not have soy allergy
- Does not have allergy to fish
- Able to participate in bi-weekly surveys in REDCap
- Able to take own blood pressure and record it in bi-weekly REDCap survey
- Willing to participate in 12-week study and be assigned to either intervention or placebo arm
- Not currently taking an omega-3 supplement or other high-dose supplement (over 2,000 IU) with potential for aiding recovery of long covid syndrome (e.g. zinc, Vit C, Elderberry).
- Able to take/swallow six mini-pills daily
- Able and willing to give a spot blood sample (2 drops) at baseline and end of study.

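### Section 17.1 makes symptom recovery the primary analysis without saying which symptoms must clear or at which survey, and Appendix C has no valid answer for a symptom that stops on study

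*Combined protocol and SAP*

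**What the plan says.** Section 17.1 (Data analysis plan) gives the test and the threshold: "The primary analysis will be the comparison of groups on the long covid-19 symptoms recovery", by a chi-square or Fisher's exact test, then "Results with a p-value less than or equal to 0.05 will be considered statistically significant". It adds "No adjustments for multiple comparisons will be implemented", because the study is a feasibility study that is not powered.

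The other relevant places are:

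- Section 4.2 says that the bi-weekly survey "includes the four symptoms being measured (respiratory, fatigue, lack of taste, lack of smell"). It does so for the secondary analysis, and gives no recovery rule and no survey.
- Section 10.0 admits subjects on this condition: "Must be experiencing 1+ ongoing covid-19 symptom being measured in this study". A subject may therefore enter with one to four of the symptoms, which must have lasted more than 12 weeks after infection.
- Section 1.0: during the 12 weeks, "subjects will be sent a survey every two weeks".
- Section 8.0: each completer is told the assigned arm by email "after the study team has seen their data (descriptive statistics generated by RedCap"), within 4 weeks of finishing.
- Section 4.1 names a different primary endpoint: feasibility and acceptability, measured by the Appendix D survey.
- Appendix C asks in which week each symptom stopped. It offers the first two weeks, the third week or the fourth week since diagnosis, still present, or never experienced.

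**The concern.** A chi-square or Fisher test needs one yes/no outcome per subject, and the plan does not define one. Because subjects bring different numbers of symptoms, an all-gone rule and an any-gone rule classify the same subject differently, and each could be read at any survey. Every such reading fits 17.1 and is judged at 0.05 without adjustment.

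The timing makes this more than missing detail. A subject enrolled at the start of month 4 (section 9.0) finishes after 12 weeks and is told the arm within a further 4. Those 16 weeks end during month 7, whereas final analysis starts in month 10. Unless the rule is fixed first, it can be chosen when outcomes by arm are knowable, and a nominal 5% result then no longer carries a 5% error rate.

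The instrument adds a second problem: whichever rule is chosen, Appendix C as printed cannot record recovery during the study for most symptoms.

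**Working it through.** **Plan's own figures.** The documents give 50 per arm for analysis (section 12.0) and a threshold of 0.05. They state no recovery rate, effect size, correlation or power, so there is no calculation to reproduce.

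**Counting the readings.**

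- Surveys: 12 weeks / 2 = 6. The documents do not print this number.
- Composite rules: all entry symptoms gone, or at least one gone = 2.
- Times: any one of 6 surveys, or ever by week 12 = 7.
- Composite readings: 2 x 7 = 14.

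Single-symptom tests are left out, because section 4.2 assigns symptom-specific effects to a separate analysis.

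**Rough guide.** If k tests were independent, the chance of at least one p <= 0.05 with no true effect would be 1 - 0.95^k. Overlapping readings are positively correlated and should generally fall below this.

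**Simulation with no true effect.** All inputs except the 50 per arm are assumptions:

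- entry prevalences of 0.60, 0.70, 0.35 and 0.35, given at least one symptom;
- recovery per symptom of 20% to 50% by week 12;
- correlation of about 0.3 to 0.5 between symptoms and 0.5 to 0.8 between surveys;
- two-sided tests.

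| Readings open to choice on results | k | 1 - 0.95^k | Simulated |
|---|---|---|---|
| One rule fixed in advance | 1 | 5.0% | about 4-6% |
| All or any, week 12 | 2 | 9.8% | about 8-10% |
| The same plus all or any, ever | 4 | 18.5% | about 14-18% |
| All 14 composites | 14 | 51.2% | about 35-48% |

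The last row is sensitive to correlation. With 0.7 between symptoms and 0.9 between adjacent surveys it was about 32%. A general check with 14 equally correlated tests gave 44%, 35% and 20% at correlations of 0.3, 0.5 and 0.8.

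**Can recovery be recorded?** Take a subject whose cough stops in study week 6. Entry required symptoms for more than 12 weeks, so the three stop options (up to the fourth week since diagnosis) are all false. Still present and never experienced are false too. A blank cannot be told from a skipped item, and Appendix C allows skipping. Section 1.0 describes infection 28 or more days earlier. Even on that wording the stop options end before the study begins, so the conclusion is the same. Fatigue alone has another route, a severity rating that includes none, and that gives it two possible definitions.

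**Do entry and follow-up match?** Appendix A (question 6) records shortness of breath and cough in one respiratory box. Appendix C lists them separately, and no mapping is given.

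**The case against.** The strongest reply is that this is a feasibility study. Section 4.1 puts feasibility first, 17.1 says the study is not powered, and leaving out a multiplicity adjustment is ordinary in a pilot. A 12-week reading is also the natural one, and most of the 14 composites depend on treating earlier surveys or ever-recovered as live candidates. Much of this stands. It is why 35-48% is only a worst case and 8-10% is the figure for the natural time point. It does not supply a definition: 17.1 still labels this test primary and calls p <= 0.05 significant, and settling the conflict with 4.1 would leave recovery undefined. The remedy asks for no adjustment, only one named contrast.

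A reader might infer three stronger things that the documents do not support:

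- *That the test as written has an inflated error rate.* It does not. Inflation needs the rule to be selected on results.
- *That the team or its analysts will see results by arm and choose accordingly.* Section 8.0 says that the team sees a completer's data before the arm is released. That the team learns the arm is inferred from its sending the email, and nothing says that analysts compare arms then.
- *That the recovery p-value decides on the larger study.* Sections 2.0 and 16.0 tie that study to feasibility and proof of concept. No go/no-go rule uses this test.

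**Conclusion.** The concern holds as a gap in specification. The primary analysis in 17.1 has no symptom rule and no survey, and the blind as described in 8.0 does not clearly protect a later choice. The size depends on conduct: about 5% for a rule fixed blind, 8-10% for a choice between all and any at week 12, 14-18% with ever-recovered added, and 35-48% if all 14 composites are tried. These figures rest on assumed recovery rates and correlations, and stronger correlation lowers the worst case. They measure the room for selection and do not predict it.

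The Appendix C defect needs no such assumptions. As printed, the stop-week item has no true answer for a symptom that resolves on study, so naming a rule in 17.1 is not enough by itself. The change should be made, and it is cheap.

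**What to change.** Before the first arm is released under section 8.0:

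1. In 17.1, name one contrast. For example: recovery means that every measured symptom present at entry is absent at the week-12 survey; omega-3 versus placebo; all randomised subjects; one two-sided test at 0.05. State how a missing week-12 survey is handled, for example counted as not recovered, with a sensitivity analysis.
2. In Appendix C, ask whether each symptom is present now. Count Appendix A's respiratory entry as resolved only when shortness of breath and cough are both absent. Say which fatigue item counts.
3. Report every other version (any symptom, single symptoms, weeks 2 to 10, ever recovered) as estimates with 95% confidence intervals and no significance label.
4. Reconcile the primary analysis in 17.1 with the feasibility primary endpoint in 4.1.

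The cost is a short amendment with IRB approval (section 20.1) and a small survey edit. An all-symptoms rule gives a lower recovery rate than an any-symptom rule, and the team gives up significance claims for other definitions. Any answers already collected on the printed item cannot be assumed to show on-study recovery.
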